7.4 Randomization (Study day 1)

Subjects that have met all criteria for study enrollment and have given written informed consent will be randomized. Subjects must meet all inclusion and no exclusion criteria at the time of randomization. The mandatory eligibility check list, provided on the CAPSIL web Portal, will be completed by the study team at the time of randomization and kept in the subject study file. The day of subject randomization is considered study day 1.

7. 4.1 Randomization procedure

Subjects that have met all criteria for study enrollment and have given written informed consent will be randomized via a web-based randomization system. Full instructions for use of the web-portal randomization procedures can be found in the Manual of Procedures. Subjects will be randomized to either prophylaxis therapy for CMV disease prevention or preemptive therapy for CMV disease prevention. The study team member randomizing the subject will get an immediate message providing group assignment.

7. 4.2 Post-randomization baseline laboratory assessments

All subjects will have the following laboratory assessments completed at the transplant center on Study day 1 prior to administration of valganciclovir.

The following laboratory assessments are anticipated to have been obtained as standard of care (SOC) and will only be drawn specifically for the study if not completed as standard care within the allowable specified window. (Standard of care values obtained within 48 hours prior to randomization may be used for baseline hematology and chemistry assessments.)

Lab values that will be collected at study day 1:

- Hematology (SOC results within 48 hours prior to randomization acceptable)
 - Hemoglobin
 - Hematocrit
 - Platelets
 - WBC with differential for absolute neutrophil calculation
(Subject will be withdrawn if ANC < 1000/ μ L at baseline)
- Chemistry (SOC results within 48 hours prior to randomization acceptable)
 - Blood urea nitrogen
 - Creatinine with Creatinine Clearance (CrCl) calculated Total bilirubin
 - AST
 - ALT
- Baseline blood sample for genetic testing (study specific evaluation)

All subjects that have agreed to genetic testing will have a onetime 10 ml sample of blood obtained at baseline. Specific consent for genetic testing will be requested at enrollment. Consent for genetic testing will be incorporated into the main consent form and will not

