8.1 Clinical Evaluations

8.1.1 Baseline demographics/medical history

Information will be recorded at the baseline study visit day 1 following randomization. Data collected will include basic demographics (information in compliance with the NIH Policy on Reporting Race and Ethnicity Data: Subjects in Clinical Research, Aug. 8, 2001 available at <http://grants.nih.gov/grants/guide/notice-files/NOT-OD-01-053.html>) gender; age, race; ethnicity. Subject weight will be recorded (weight recorded is the most recent weight obtained as standard care or obtained by the investigator). Also collected will be specific medical information including date of liver transplant, donor age and type (living or deceased), most recent standard of care MELD score prior to transplant, underlying liver diseases leading to transplant and co-morbid conditions (diabetes, cancer, cardiovascular disease, respiratory disease, renal disease). Specific baseline medications will be recorded including immunosuppressive agents, drugs with known hematologic toxicity, and any doses of antiviral agents. Standard of care clinical laboratory results, donor CMV serology, and study specific laboratory results will be recorded. All data will be abstracted from the medical records. Only current medical records from the transplant admission will be reviewed for baseline data collection. No past medical records will require review with the exception of confirmation of CMV serostatus with-in the allowable study window. No study specific physical examination will take place.

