12.6.1.3 Bacterial, fungal and non-CMV viral infections

Invasive fungal infections, major bacterial infections and non-CMV viral infections will be analyzed. These infections are outlined in the manual of operations. The analysis of incidence of an opportunistic infection will be performed using a Chi Square test or Fisher Exact in the modified ITT population. Results will be reported as the p -value and the 95% confidence interval for the difference in the rates of invasive fungal, major bacterial or viral infections; the analysis will be repeated using a CMH test stratified by receipt of induction therapy. The analysis will include an assessment of baseline comparability of the comparison groups and will incorporate variables not adequately controlled by randomization. The initial episode of major infection will be evaluated in a time dependent Cox model with the end point being the date of first major infection. The starting point will be date of transplantation and the infection free survival functions will be compared between the two regimens adjusted for cluster [site]. Subjects will be censored at death and study termination/withdrawal. Multiple infection episodes will be evaluated by comparing the total 1 year episodes per person day of follow up between the two regimens. The analysis will be repeated controlling for receipt of anti-lymphocyte induction and renal dialysis. The type of infection (major bacterial, fungal, non- CMV viral) will be compared between the two regimens using a CMH test, non-stratified and controlled for induction antilymphocyte therapy and renal dialysis. Summary tables listing the type of opportunistic infections for each regimen will be presented.

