12.6.2 Hematologic toxicity

12.6.2.1 Incidence of neutropenia

The incidence of neutropenia will be summarized for each of the following definitions of neutropenia: ANC values < 1000/ μ L and < 500/ μ L. Incidence will be determined based on safety labs performed per protocol. The analysis will be a CMH test of the significance of the odds ratio, while controlling for anti-lymphocyte antibody induction and renal dialysis with the levels of stratification determined at the time of randomization, using the modified ITT population. Results will be reported, as the MH odds ratio with 95% confidence intervals in the modified ITT population. The analysis will include assessment of baseline comparability of the comparison groups and will incorporate relevant items not adequately controlled by randomization in additional models.

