12.7 Exploratory end-points

12.7.1 Clinical outcomes

12.7.1.1 Time to onset of CMV disease

Disease free survival will be evaluated by calculating the Kaplan-Meier survival probability for each regimen. The starting point will be the day of transplant; the end point will be the date of onset of CMV disease. Subjects will be censored at date of death if unrelated to CMV, date of last follow up if lost to follow up or at end of study. Kaplan-Meier estimates of median time to onset of CMV disease and the associated 95% confidence interval will be presented. In addition, the Kaplan-Meier estimates and associated confidence intervals will be presented for specific time points (100-day, 6-month 12-months) and quartiles (25th and 75th). The study groups will be compared using the non-stratified log rank test, as well as the stratified log rank test for each stratum separately. Graphs of the Kaplan-Meier curves for each therapy group will be presented. The equality of the two survivor functions will also be compared using a Cox model adjusted for cluster [site] and controlled for receipt of anti-lymphocyte induction therapy and renal dialysis. The primary analysis will include assessment of baseline comparability between the two treatment groups. If needed, additional models will be developed to adjust for inequalities not adequately controlled by the randomization process. Results will be reported as the hazard ratio comparing the 2 groups. Survival analyses will also be controlled for unequal follow up periods between subjects. As such, the number of subjects available at annual time points will be reported, along with the Kaplan-Meier probability and associated 95% confidence intervals. It is assumed that subjects censored early will have the same probability of disease at each time point as those with longer follow up. To examine this assumption, relevant baseline characteristics will be compared between subjects enrolled in the first half of the study with those enrolled later. If the 2 cohorts are similar, we can expect that the survival probabilities are valid even with difference in follow up. Disease free survival will also be examined between the two cohorts.

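### Section 12.6.1.3 selects infection covariates by observed baseline imbalance instead of fixing prognostic ones in advance; six other sections repeat the rule, mostly for optional extra models

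*Combined protocol and SAP*

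**What the plan says.** Section 12.6.1.3 starts with a test that takes no covariates: "The analysis of incidence of an opportunistic infection will be performed using a Chi Square test or Fisher Exact in the modified ITT population". It continues: "the analysis will be repeated using a CMH test stratified by receipt of induction therapy". The next sentence is the one at issue: "The analysis will include an assessment of baseline comparability of the comparison groups and will incorporate variables not adequately controlled by randomization". Later the section adjusts a Cox model for site and, for multiple episodes, adds: "The analysis will be repeated controlling for receipt of anti-lymphocyte induction and renal dialysis". The infection-type comparison is likewise run with and without control for induction and dialysis. These fixed adjusters are the randomization factors (sections 5.4.2 and 12.2).

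The same idea appears elsewhere. For neutropenia (12.6.2.1) the analysis "will incorporate relevant items not adequately controlled by randomization in additional models". For time to CMV disease (12.7.1.1), where needed, "additional models will be developed to adjust for inequalities not adequately controlled by the randomization process". Sections 12.6.1.4, 12.6.3, 12.7.1.4 and 12.7.1.5 carry close variants. None names candidate variables, a threshold, or the time at which the choice is made.

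Prognostic data are collected. Section 8.1.1 records recipient age, donor age and type, and the "most recent standard of care MELD score prior to transplant". Section 7.4.2 records "WBC with differential for absolute neutrophil calculation" at baseline. None of these enters a fixed model.

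**The concern.** Precision in an adjusted analysis depends on how strongly a covariate predicts outcome, not on whether it happens to differ between arms. A rule driven by imbalance can admit an irrelevant variable that differs by chance and leave out a strong predictor that is well balanced. It also leaves the adjusted model undefined until the data are in. The trial is open label, the blinded endpoint committee judges CMV disease only, and nothing says that the person choosing covariates is blinded. At stake are some unused precision for secondary endpoints and some room to choose among results. In 12.6.1.3 the sentence also cannot be programmed as written: the first-named test accepts no covariates, and the text does not say which of the later analyses should take them.

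**Working it through.** **1. The plan's own figure.** Power is given only for the primary endpoint: 80 per group, 20% versus 5%, 80% power (section 12.1). Exact enumeration of the two-sided Fisher test at 80 per group gives 79.3%. Freedman's formula at hazard ratio 0.229 gives 20 events, and 20 / ((0.20 + 0.05)/2) = 160 subjects. The figure reproduces, but the present point does not depend on it. The documents give no power for infection or neutropenia and no covariate effects, so steps 3 and 4 rest on assumptions.

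**2. Where the clause applies.**

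| Section | Endpoint | Status of the imbalance clause |
|---|---|---|
| 12.6.1.3 | Infections (secondary) | In the analysis itself |
| 12.6.1.4 | Rejection (secondary) | One optional additional model |
| 12.6.2.1 | Neutropenia (secondary) | Additional models |
| 12.6.3 | Adverse events | Additional models, if necessary |
| 12.7.1.1, 12.7.1.4, 12.7.1.5 | Time to CMV disease; graft loss to closure (exploratory) | Additional models, if needed |
| 12.5.4 | Primary CMV disease | Absent |
| 12.6.1.1, 12.6.1.5, 12.6.1.6, 12.7.2.1 | Late-onset CMV, 12-month graft loss, mortality, G-CSF use | Absent |

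Of the seven secondary outcomes in section 3.2.2, three carry the clause.

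**3. How often the rule would act.** With K independent covariates each tested at level a, the chance that at least one is flagged is 1 − (1 − a)^K. At a = 0.10 and K = 5 this is 1 − 0.9^5 = 41%; K = 8, 10 and 15 give 57%, 65% and 79%. At a = 0.05 the four values are 23%, 34%, 40% and 54%.

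**4. Power and type I error by simulation.** Assumptions: 176 subjects (the minimum enrollment), 88 per arm; logistic model; control infection rate 35% at average covariate values; treatment odds ratio 0.42; eight independent covariates, two of them prognostic; imbalance flagged at p < 0.10; 3,000 runs. Monte Carlo error is about 0.9 points for power.

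| Covariate odds ratio per SD | Unadjusted | Imbalance-selected | Two prognostic covariates fixed | Fixed minus selected |
|---|---|---|---|---|
| 1.5 | 65.8% | 66.0% | 68.3% | 2.3 |
| 2.0 | 59.6% | 61.1% | 67.7% | 6.6 |
| 2.5 | 51.5% | 51.9% | 62.3% | 10.4 |

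Other settings at the same sample size:

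- Infection-type endpoint, five covariates, three prognostic at log-odds 0.5 per SD: 67.0% selected, 71.8% fixed, a gain of 4.8 points.
- Infection with log-odds 0.25 per SD: 67.9% unadjusted, 68.0% selected, 68.4% fixed, a gain of 0.4.
- Neutropenia, assumed 15% control rate, baseline ANC at log-odds 0.3 per SD: 71.2%, 70.5% and 70.9% in the same order, effectively no difference.
- Neutropenia, ANC at log-odds 1.0 per SD, treatment log-odds −1.3: 80.2%, 80.7% and 85.4%. The control rate behind this run is not stated, so it shows direction only.

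Under the null, in the eight-covariate setting, the rule applied mechanically rejects in 4.4% to 4.8% of runs. Citing the better of the unadjusted and imbalance-adjusted results gives 5.7% in the five-covariate setting. Taking the smallest p-value among the unadjusted, imbalance-selected and eight single-covariate models gives 7.6% to 8.2%.

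**The case against.** The strongest reply is that a defensible result already exists for each of these endpoints. Infections have an unadjusted test and strata-adjusted repeats, rejection and neutropenia have fixed CMH tests, and outside 12.6.1.3 the imbalance clause governs only additional models. That stands, and it keeps the point small.

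Four stronger readings are tempting, and the documents support none of them.

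- A reader might infer that the primary comparison is exposed. Section 12.5.4 has no such clause. Section 12.7.1.1 does mention a primary analysis beside its baseline-comparability check, but that section concerns exploratory time to CMV disease.
- A reader might infer that every secondary result comes in two versions. The table in step 2 shows otherwise.
- A reader might infer that the rule costs power or inflates error by itself. Selected-covariate power is close to unadjusted power in every setting, and mechanical use keeps type I error at or below 5%. What is forgone is a possible gain.
- A reader might infer that covariates will be picked after outcomes by group are known. The text speaks of baseline comparability, which needs no outcome data, and it does not give the timing. The discretion is open, but its misuse is not planned.

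It is also fair to say that the gain is assumed: with weak covariates it vanishes. Section 12.6.1.1 does refer to prognostic factors, but only for late-onset CMV disease, and its one example, rejection, arises after randomization. It does not fill the gap.

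**Conclusion.** The point holds as a low-cost improvement to secondary and exploratory analyses. The plan states a selection criterion that is inferior to fixing prognostic covariates it already collects; 12.6.1.3 is the clearest case because there the rule sits in the analysis itself. Against imbalance selection the gain from a fixed list is roughly 0 to 10 points of power. That range depends on an assumed 35% infection rate, an odds ratio of 0.42 and covariate strengths that the documents do not supply, so it should not be quoted as a loss suffered by this trial. The error risk comes from unrestricted choice among models, about 5.7% for the better of two results and up to about 8% with wider choice.

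**What to change.** Before outcomes by group are seen, replace the imbalance-driven adjustment with a short fixed list, used whatever the observed balance:

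- **Infection:** induction and dialysis, with site handled as already planned, plus MELD, recipient age and donor type.
- **Neutropenia:** induction, dialysis and baseline ANC.
- **All affected endpoints:** state which analysis is the main one, and label any imbalance-driven model as sensitivity only.
- **Sparse endpoints (retransplantation, ANC below 500):** keep the strata-adjusted CMH test, or add at most one covariate. Section 6.2.5 expects under 2% retransplantation after day 30, that is fewer than 0.02 × 176 = 3.5 subjects. The neutropenia rates in section 2.3.1.2 run from 1.2% to 15%, or about 1 to 13 events per 88 subjects, so the neutropenia model needs the same caution if events are few.

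The cost is SAP wording, since every variable is already collected. The downsides are up to three more parameters per model, and a conditional odds ratio where 12.6.1.3 reports a difference in rates; standardizing over the fitted model would recover that difference.

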12.6.1.4 Allograft rejection

Rejection will be evaluated by several methods. Rejection rates at one year, between the two groups will be evaluated with a CMH test, both non-stratified and adjusted for receipt of antilymphocyte induction and renal dialysis. Initial rejection will be evaluated in a time dependent Cox model with the end point being the date first rejection episode. The starting point will be date of transplantation and the rejection free survival functions will be compared between the two regimens adjusted for cluster. Multiple rejection episodes will be evaluated by comparing the total 1 year episodes of rejection between the regimens using a regression model with the endpoint total number of rejection episodes, clustered by site, and adjusted for receipt of antilymphocyte induction therapy and renal dialysis. An additional model may be developed to adjust for inequalities not adequately controlled by the randomization process. Incidence of chronic graft rejection will be compared between the two study groups using a CMH test stratified for receipt of induction lymphocyte depleting therapy and controlling for renal dialysis.

Rejection episodes

Incidence rates will [number of rejection episodes per patient days of follow up] will be calculated and compared between the two groups. Patient days will be counted from the day of

randomization until the date of death, one year or last known follow up if subject is unable to be followed for one year.

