12.7.1.4 Graft loss [retransplantation]

A Kaplan-Meier survival probability will be calculated for each regimen. The starting point will be the day of transplant; the end point will be the date of retransplant. Subjects will be censored at date of last follow up if lost to follow up, at date of death, or at study closure (and no longer than 7 years after enrollment). The equality of the two survivor functions will be compared using a rank sum test. Additional models will include adjustment for cluster [site] and receipt of antilymphocyte induction therapy and renal dialysis. The analysis will include assessment of baseline comparability between the two treatment groups. If needed, additional models will be developed to adjust for inequalities not adequately controlled by the randomization process.

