12.7.1.5 Graft loss [death]

A Kaplan-Meier survival probability will be calculated for each regimen. The starting point will be the day of transplant; the end point will be the date of retransplant or date of death if no retransplantation occurs. Subjects will be censored at date of last follow up if lost to follow up, or at study closure (and no longer than 7 years after enrollment). The equality of the two survivor functions will be compared using a Cox model. The survival functions will also be presented adjusted for cluster [site] and stratified by receipt of antilymphocyte induction therapy and renal dialysis. The analysis will include assessment of baseline comparability between the

two treatment groups. If needed, additional models will be developed to adjust for inequalities not adequately controlled by the randomization process

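### Six supplementary or exploratory models treat the six sites as clusters without naming a variance, although subjects are randomized individually within site; on one plausible reading nominal 5% Cox tests run at about 9–16%

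*Combined protocol and SAP*

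**What the plan says.** The Protocol Summary gives six clinical sites. Sections 5.4.2 and 12.2 randomize individual subjects 1:1, stratified at each site by lymphocyte-depleting induction and dialysis. Section 12.4.1 sets tests at two-sided 0.05 unless stated otherwise and allows either of two software packages.

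Site is then called a cluster in six places:

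- 12.6.1.3, first major infection (Cox): "the infection free survival functions will be compared between the two regimens adjusted for cluster [site".
- 12.6.1.4, first rejection (Cox): "the rejection free survival functions will be compared between the two regimens adjusted for cluster".
- 12.6.1.4, number of rejection episodes (a regression model of unstated type): "clustered by site, and adjusted for receipt of antilymphocyte induction therapy and renal dialysis".
- 12.7.1.1, time to CMV disease: the curves "will also be compared using a Cox model adjusted for cluster [site] and controlled for receipt of anti-lymphocyte induction therapy and renal dialysis". This follows an unadjusted comparison: "The study groups will be compared using the non-stratified log rank test".
- 12.7.1.4, retransplantation, after an unadjusted rank sum test: "Additional models will include adjustment for cluster [site] and receipt of antilymphocyte induction therapy and renal dialysis". No model type is given.
- 12.7.1.5, retransplantation or death: "The equality of the two survivor functions will be compared using a Cox model". The survival functions are then also to be shown "adjusted for cluster [site] and stratified by receipt of antilymphocyte induction therapy and renal dialysis".

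None of these places names a variance estimator, a correction for few clusters or a reference distribution.

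**The concern.** Each site contributes subjects to both arms by design, so differences in event rate between sites largely cancel out of the treatment comparison. Site is a stratum of the randomization, not the unit that was allocated. If cluster adjustment means a cluster-robust (sandwich) variance, that variance is estimated from only six site totals. It is then too small on average and too variable for a normal critical value, and chance differences reach p<0.05 two to three times as often as stated.

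The reading is plausible. It is the natural one for the rejection-count model in 12.6.1.4. Section 12.7.1.1 also uses one verb for site and another for induction and dialysis. For major infection and rejection, both secondary endpoints, the cluster model is the only time-to-first-event comparison that the plan names.

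**Working it through.** **Anchor.** The plan states no error rate for these models. Its time-to-event convention can be reproduced from section 12.1: hazard ratio ln(0.95)/ln(0.80) = 0.230; events by Freedman's formula (1.960 + 0.842)² × (1.230/0.770)² = 20.0; N = 20.0/0.125 = 160. These match the stated 20 events and 160 subjects.

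**Approximation for six equal sites.** With G = 6, a robust statistic that carries the factor G/(G−1) behaves roughly as t on G−1 = 5 degrees of freedom.

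- With the factor, normal critical value: P(|t₅| > 1.96) = 10.7%.
- Without the factor: the threshold is in effect 1.96 × √(5/6) = 1.79, and P(|t₅| > 1.79) = 13.4%.
- The t critical value on 5 df is 2.57, not 1.96.

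**Null simulation, Cox model with treatment only.** From the documents: six sites, N = 176 or 205, 1:1 blocked allocation within site, two-sided 5%. Assumed: blocks of 4, about 10% early censoring, site log-hazard SD 0 or 0.5, event rates 8–50%, and the site splits shown. There were 4,000 trials per setting. Rejection rates (%):

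| Site split | Robust, no factor, 1.96 | Robust, G/(G−1), 1.96 | Robust, G/(G−1), t on 5 df |
|---|---|---|---|
| Equal | 11.7–13.6 | 8.9–10.8 | 3.3–5.0 |
| 30/25/15/12/10/8% | 13.3–15.2 | 10.2–12.6 | 4.4–6.0 |
| 45/20/12/10/8/5% | 15.6–17.9 | 12.5–14.9 | 5.6–7.9 |

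A Cox model stratified by site, with model-based variance, gave 4.1–5.0% (event rates 20% and 50%).

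**Second null simulation, adjusted for induction and dialysis.** N = 176; sites of 29–30 each or 60/40/30/20/16/10; induction 20% and dialysis 15%, each with hazard ratio 1.5 (assumed); 3,000 trials per setting; event rates 8–50%. In the column order above: 11.5–15.9%, 8.7–12.7% and 3.7–6.2%. Stratified by site: 3.5–5.7%. Monte Carlo standard error is about 0.4–0.7 points.

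**Rejection counts, simulated separately** (0.25 or 0.5 episodes per subject, assumed), same column order:

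- Linear: 11.5–16.2%, 8.9–13.1%, 3.8–6.7%; with site fixed effects 4.3–5.6%.
- Poisson: 13.5–18.5%, 10.6–14.9%, 4.6–7.8%; with site fixed effects and scaled variance 4.1–6.3%.

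**Rare retransplantation.** Section 6.2.5 expects under 2% after day 30; 0.02 × 176 is about 3.5 subjects. At a 3% event rate the adjusted Cox model could be fitted in only 49–52% of trials, and the normal-critical-value tests then ran at 4.6–11.9%. At 5% it fitted in 73–77%, with 5.9–14.3%. An unadjusted log-rank test, standing in for the rank sum test of 12.7.1.4, held 3.5–4.8% at event rates of 2–5%.

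**Under a real effect.** At hazard ratios of 0.23 or 0.55, nominal 95% intervals covered 85–94% (robust, normal critical value) against 95–97% (site-stratified). Power at 20% v 5% was 83–86% site-stratified against 60–66% for the robust variance with t on 5 df. At hazard ratio 0.55 with a 40% control rate it was 57–60% against 38–45%.

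**The case against.** The strongest reply is that no section mentions a robust variance or a normal critical value. If site enters as a stratum, covariate or frailty with model-based variance, the inflation does not follow. That stands: what is shown is an unspecified method, not a plan that commits to a faulty test. Section 12.7.1.4 lists site beside the covariates, which fits an ordinary site term. Section 12.7.1.5 speaks of presenting adjusted survival functions, and a robust variance does not change a curve. That sentence also announces a presentation rather than a separate test.

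A reader might apply 9–16% to all six places. The documents do not support that: the rejection-count model is not a Cox model, and retransplantation is expected to be rare and has no stated model type.

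A reader might also infer that the efficacy conclusion is at risk, or that section 12.5.4 needs rewriting. It does not: the primary CMH analysis carries no cluster term. Infection also has a Chi-square/Fisher test and rejection has CMH tests. Sections 12.7.1.1, 12.7.1.4 and 12.7.1.5 each name an unadjusted comparison first.

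**Conclusion.** The concern holds as a conditional one, at minor severity. The plan leaves open what cluster adjustment for six sites means. On a plausible reading, a cluster-robust variance with a normal critical value, nominal 5% Cox tests run at about 9–16% for equal to moderately unequal sites and event rates of 8–50%, and up to about 18% with very unequal sites. The rejection-count model shows similar inflation. The range does not carry over to rare retransplantation.

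The figures rest on assumed site sizes, event rates, block size and between-site variation; the documents give none of these for the models concerned. A frailty model was not simulated, but it would use a model-based variance. The effect is confined to supplementary and exploratory results; the primary analysis and the sample size are untouched.

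**What to change.** Change the wording before the one-year analysis:

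- **12.6.1.3, 12.6.1.4 (first rejection) and 12.7.1.1:** specify a Cox model stratified by site with the model-based variance, with induction and dialysis as covariates where the plan already controls for them.
- **12.7.1.5:** stratify by site and enter induction and dialysis as covariates. Stratifying by all three gives up to 6 × 2 × 2 = 24 strata. In simulation about 20–21 were occupied, 25–30% of these held two or fewer subjects, and power fell 2–4 points below site stratification alone.
- **12.6.1.4 (rejection counts):** use site fixed effects with an overdispersion-scaled variance, and state that sites with no episodes drop out.
- **12.7.1.4:** rely on the unadjusted test already planned, because few events are expected.

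The cluster-robust variance with t on 5 df should not be offered as an equal alternative. It lost 13–26 points of power in the settings above and still reached 7.9% with very unequal sites.

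The cost is small, since site, induction and dialysis are already recorded. Site-stratified intervals are about 1% wider than those of a Cox model without site, with power within −1 to +3 points. They are 13–23% wider than uncorrected cluster-robust intervals, but only because those are too short.
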